### 16.4 Management of Identifiers:

- Identifiers will be destroyed after all data has been collected.
- Identifiers will be destroyed at study closure.
- Identifiers will be destroyed at study closure or at the time of publication.

### 16.5 Plans for sharing of data and/or specimens outside the study team / institution:

## PROTOCOL TITLE: SAFE AND HEALTHY SCHOOLS

Exact Sciences or ACL will provide us with the results of the nasal swab PCR test collected by the school. The study team will provide lollipop collection swabs to Exact Sciences or ACL for analysis.

To obtain the nasal swab PCR test results from Exact Sciences, the study team will send Exact Sciences a result pull request with the participant's name, date of birth, and collection date. We will do this by uploading information to Exact Sciences' HIPAA-secure Box for sharing with Exact. The lollipop collection swabs will be labeled with the participant's study ID and date of collection.

To obtain the nasal swab PCR test results from ACL, the study team will include information on the lollipop swab label and accompanying requisition form, including the participant's name, date of birth, and date and time of collection. ACL will match this information to a nasal swab and provide PCR test results for both the lollipop and nasal swab.

The results of the nasal swab and lollipop PCR tests will be sent via Exact Sciences' HIPAA-secure Box or a UW-Madison Cybersecurity-approved data sharing tool.

A study team member will deliver the lollipop swabs from the school to Exact Sciences or ACL.

## 17.0 Provisions to Protect the Privacy Interests of Participants

### 17.1 Steps that will be taken to protect participants' privacy interests:

- Procedures will be performed in a private area where others cannot see the procedures being performed or overhear the conversation between subjects and researchers.
- All members of the study team are up to date on their institutional HIPAA training.
- The study is not collecting information that could pose legal or reputational risks to participants.

### 17.2 To conduct research on COVID-19 testing methods, it is necessary to collect participant's communicable disease status, which is considered sensitive information.

### 17.3 Study team members will be experienced and/or trained in how to work with children and help them feel at ease during research procedures. Study team members will explain study procedures to participants in advance using age-appropriate language, and they will take time to answer any questions that participants may have.

## 18.0 Sharing of Results

## PROTOCOL TITLE: SAFE AND HEALTHY SCHOOLS

18.1 Since the lollipop PCR test is investigational, the results will not be shared with participants or others. If the at-home BinaxNOW test is positive, the study team member will encourage the participants to follow up with their primary care provider. The school will receive the results of the nasal PCR from Exact Sciences or ACL, and that result will govern whether the child is permitted to return to school when symptoms resolve (if PCR is negative) or is required to stay at home for 10 days (if PCR is positive). As the resulting lab, Exact Sciences and ACL are responsible for reporting the nasal PCR results to Dane County Department of Health Services. Since the lollipop swab is investigational, results do not need to be reported to health officials.

For overall care management and recommendations, the study team is deferring to the school, which conducts and receives results of the nasal swab PCR result. Since this is the clinical test, the investigators would not recommend changing care management based on the exploratory test results in this study (lollipop swab and BinaxNOW). Any time an at-home BinaxNOW test is positive, the study team will encourage participants to follow up with the school and/or their PCP for recommendations. In short, the overall care plan will be based on the nasal swab PCR and managed by the school.

18.2 The results of this study will be published and accessible to the public.

## 19.0 Data and Specimen Banking

19.1 The lollipop swabs and assays will be destroyed after results are recorded. Participants will be instructed to dispose of BinaxNOW test cards after the test is completed. There will be no biospecimen banking in this study. All data for this study will be stored in Exact Sciences' HIPAA-Secure Box, a UW-Madison Cybersecurity-approved data sharing tool, Department of Pediatrics Secure Server, and REDCap, and only approved study team members will have access to the REDCap project.

19.2 At the end of this study, participant names and contact information (phone, address, email) will be destroyed. All other study data will be banked.

19.3 Only de-identified data will be shared with external researchers.

19.4 Data will be fully anonymized prior to banking, so participants may not withdraw their banked data from future research use.

## 20.0 Study Analysis

20.1 Statistical Hypotheses:

Aim 1: The null hypothesis is that the negative predictive value of BinaxNOW is at least 91% (which is the reported rate in symptomatic

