## PROTOCOL TITLE: SAFE AND HEALTHY SCHOOLS

subjects after a single test) versus the alternative hypothesis that the NPV is greater than 91%.

Aim 2: The lollipop swab test will be non-inferior to the gold-standard PCR testing of nasal swabs.

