### 20.2 Sample Size Justification:

For Aim 1, it is anticipated that the majority of initial BinaxNOW tests will be negative. It is hypothesized that the proposed two-day serial testing procedure using BinaxNOW tests in participants with an initial negative test will identify true negatives in >95% of participants. The primary diagnostic outcome measure will be the negative predictive value (NPV). The NPV of BinaxNow is ~91% in symptomatic subjects. For the proposed study, the NPV after the second test (24 hours after the first negative results), is assumed to be substantially higher than 91% since the first test was already negative. In order to detect a true NPV after the second test of at least 95% with 90% power at the one-sided 0.05 significance level, a sample size of N=358 participants with an initial negative test is required. To reach a sample size of N=358 participants with an initial negative test, BinaxNOW kits will be administrated to 400 participants. We intend to continue enrolling until we reach the target sample size of N=358 completing the at-home BinaxNOW test.

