### 20.3 Participant Population for Analysis:

For Aim 1, we will include all participants who complete the at-home BinaxNOW test within 72 hours (N=358) and have nasal PCR results. For Aim2, we will include all participants who have both nasal and lollipop PCR results.

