### 20.4 Statistical Methods:

**Aim 1.** Sensitivity, specificity, positive predictive value (PPV) and NPV of the proposed BinaxNOW testing procedure for symptomatic subjects will be calculated and reported along with the corresponding two-sided 95% confidence interval. Formal non-inferiority testing of the BinaxNOW testing procedure with PCR will be conducted with respect to sensitivity and specificity with a non-inferiority margin of  $\delta=5\%$  and a sensitivity/specificity of PCR of 99%.

**Aim 2.** Results obtained from nasal and lollipop swab-based PCR testing will be summarized in tabular format. Concordance between the PCR test results will be evaluated by calculating the Kappa statistic which will be reported along with corresponding two-sided 95% confidence interval. The nonparametric bootstrap technique will be used to construct the confidence interval. A kappa statistic of  $>0.95$  will be considered as sufficient to define lollipop swab test non-inferior to the gold-standard PCR testing of nasal swabs. Furthermore, standard diagnostic test outcomes, i.e., sensitivity, specificity, NPV and PPV will be calculated (using the nasal swab-based

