## 21.0 Potential Benefits to Participants

21.1 For participants who only participate in the lollipop PCR portion of the study, there is no immediate benefit.

Through doing the at-home BinaxNOW testing under the observation of a trained study team member, participants and their families may learn about how to accurately conduct this type of at-home test for COVID-19. Through asking questions and/or receiving confirmation that they are conducting the test correctly, individuals and families may feel more confident conducting at-home tests in the future. If the second test in the BinaxNOW kit is not used as a back-up during the study, the participant may keep the test and use it later if they feel comfortable doing so. The BinaxNOW tests are also readily available to families at local retailers, such as Walgreens. Therefore, if a family member is symptomatic in the future, they may feel more comfortable doing at-home testing independently.

The results of the BinaxNOW test, along with other information, can help participants' healthcare providers make informed recommendations about their care. For example, in the case that the original BinaxNOW and nasal swab PCR tests were negative and the delayed, at-home BinaxNOW test is positive, that would be helpful information for a participant's primary care provider. That information will need to be integrated with the results of the nasal PCR that was also performed. The probability that the delayed, at-home BinaxNOW test will be positive is less than 5%.

If the results of the at-home BinaxNOW test are negative, that may help individuals and families feel more confident in the initial results they received.

The results of the at-home BinaxNOW test in this study, or any future at-home BinaxNOW tests that families may conduct, may help limit the spread of COVID-19 to participants' families and others in their community.

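### The Aim 1 null contains its own alternative, and beating a fixed 91% NPV does not by itself show that the second BinaxNOW test adds anything

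*Combined protocol and SAP*

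**What the plan says.** Section 20.1 states for Aim 1 that "The null hypothesis is that the negative predictive value of BinaxNOW is at least 91" per cent, a figure it describes as the reported rate in symptomatic "subjects after a single test) versus the alternative hypothesis that the NPV is greater than 91" per cent.

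Section 20.2 makes NPV the main measure: "The primary diagnostic outcome measure will be the negative predictive value (NPV"). It gives the single-test NPV in symptomatic people as about 91% and says that the NPV after the second test "is assumed to be substantially higher than 91% since the first test was already negative". It then sizes the study: "In order to detect a true NPV after the second test of at least 95% with 90% power at the one-sided 0.05 significance level", N = 358.

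Section 20.3 defines the Aim 1 set: "we will include all participants who complete the at-home BinaxNOW test within 72 hours (N=358) and have nasal PCR results". Section 5.2 adds that these participants had a negative at-school BinaxNOW.

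Section 20.4 reports sensitivity, specificity, PPV and NPV with 95% confidence intervals, and says "Formal non-inferiority testing of the BinaxNOW testing procedure with PCR will be conducted with respect to sensitivity and specificity", with a 5-point margin and PCR taken as 99%. It plans no comparison with first-test NPV in the same people.

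**The concern.** There are two separate faults.

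**Wording.** Any NPV above 91% is also an NPV of 91% or more. As written, the alternative is part of the null, and no result could reject one in favour of the other. The primary hypothesis also contradicts the test sized in 20.2.

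**Benchmark.** A single-test NPV is the probability of being uninfected given a negative first test. That describes everyone in the Aim 1 set, so having had a negative first test is no reason for NPV to exceed a single-test figure. What could raise it is the second test catching infections the first one missed. The planned test does not isolate that, because NPV also rises when fewer participants are infected, and section 2.3 calls prevalence in the study year unknown.

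The plan invites reading a pass as a gain: 20.2 gives the rationale above, and 2.3 expects a repeat test to turn positive almost always in an infected person. A published result of NPV above 91% on the primary, sized test could therefore be taken as evidence for home retesting when it reflects only low infection among initial negatives. Nor would it show non-inferiority to PCR, which only the sensitivity and specificity tests in 20.4 address.

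**Working it through.** **Inputs from the documents.** Benchmark 0.91, target 0.95, one-sided alpha 0.05, power 90%, N = 358 (20.2); PCR accuracy 99% and margin 5% (20.4); BinaxNOW sensitivity about 94% (2.3); at-home positives below 5% (21.1). **Assumed:** PCR-positive share q among initial negatives from 4% to 9%, and second-test specificity sp from 0.98 to 1.

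**1. The plan's own N.** For an exact binomial test of NPV ≤ 0.91 at n = 358, reject at 335 or more: P(X ≥ 335 | 0.91) = 0.0487 and P(X ≥ 335 | 0.95) = 0.909. No n from 250 to 357 reaches 0.90. So 358 is reproduced with 0.91 as the upper edge of the null.

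**2. A second test that always reads negative.** All 358 are then second-test negative and NPV = 1 − q. It passes with 358 − 335 = 23 or fewer PCR-positives, with probability P(Bin(358, 1 − q) ≥ 335):

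| q | 9% | 8% | 7% | 6% | 5% | 4% |
|---|---|---|---|---|---|---|
| P(pass) | 0.049 | 0.158 | 0.384 | 0.683 | 0.909 | 0.990 |

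**3. Same sample, very different second tests.** Take 18 PCR-positives (5%) and 4 false positives. First-test NPV = 340/358 = 0.950. Second-test true negatives = 340 − 4 = 336.

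| Detected of 18 | Second-test NPV | Exact p against 0.91 | NPV gain, points (bootstrap 95% CI) | Missed per 100 after the second test |
|---|---|---|---|---|
| 0 | 336/354 | 0.004 | −0.1 | 5.0 |
| 2 | 336/352 | 0.001 | 0.5 (−0.1 to 1.3) | 4.5 |
| 9 | 336/345 | 1.6 × 10⁻⁶ | 2.4 (1.0 to 4.1) | 2.5 |
| 17 | 336/337 | 5 × 10⁻¹³ | 4.7 (2.8 to 7.0) | 0.3 |

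All four pass. Missed infections before the second test are 18/358 = 5.0 per 100. The gain separates the four; the 91% test does not.

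**4. Detection needed to reach 95%.** Second-test NPV = (1 − q)sp / [(1 − q)sp + q(1 − se)]. Setting this to 0.95 gives se = 1 − (1 − q)sp/(19q). At q = 0.09, where the 91% benchmark is exactly right, se = 1 − 0.91/1.71 = 0.468 (0.478 at sp = 0.98), about 15 of 32. At q = 0.07 it is 0.30 to 0.31; at q = 0.05, 0.00 to 0.02. The 20.4 threshold is 99% − 5% = 94%.

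**5. Is a low share plausible?** Section 21.1 says "The probability that the delayed, at-home BinaxNOW test will be positive is less than 5" per cent. If that covers all initial negatives (it follows an example about PCR-negative participants), then 0.94q + (1 − q)(1 − sp) < 0.05. This gives q below 5.3% at sp = 1, 4.3% at 0.99 and 3.3% at 0.98, where the always-negative test passes with probability 0.853, 0.977 and 0.999. If the second test detects only 50%, the bound at sp = 1 loosens to 0.05/0.50 = 10%, where that test passes with probability about 0.01.

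**6. Can the sensitivity test carry the conclusion?** Section 20.4 names no test or alpha. At an assumed one-sided 0.05 with perfect detection, a score test against 0.94 needs n ≥ 1.645² × 0.94 × 0.06/0.06² = 42.4, so 43 PCR-positives. The exact test needs 49 (0.94⁴⁸ = 0.051; 0.94⁴⁹ = 0.048). Expected numbers are 0.09 × 358 ≈ 32 and 0.05 × 358 ≈ 18. The chance of 43 or more at q = 9% is 0.03.

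**The case against.** **The wording slip changes nothing in practice.** The alternative is stated correctly, 20.2 sizes the right test, and any statistician would run NPV ≤ 91%. This is true, and it is why the first part is a correction of text only.

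**The plan never claims that passing 91% shows a benefit.** Aim 1 is feasibility and non-inferiority to PCR. It is fair that the reading is inferred from 20.2 and 2.3. But NPV is the primary measure and the only sized test, so it needs a stated interpretation.

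**Section 20.4 already exposes a useless second test.** Because everyone is first-test negative, sensitivity in this set is the share of first-test misses that the second test catches. In the 18-positive examples its exact 95% intervals are 0–19%, 1–35%, 26–74% and 73–99.9%. NPV gain is arithmetic on the same 2×2 table. This stands, and limits the point to what NPV shows by itself. What is missing is the side-by-side report and a rule for reading it.

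**If first-test NPV really is 91%, the benchmark works.** An always-negative test then passes at 0.049, which is just alpha. Correct; the large probabilities need shares of about 4% to 6%, which the documents do not give outright.

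**The gain has its own limits.** PCR is taken at school and the home test about a day later, so an infection emerging in between counts as a false positive and lowers the gain. With few positives it is imprecise. Both stand and argue for reporting it descriptively.

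**Conclusion.** Both parts hold. The null in 20.1 is wrong as written, and correcting it leaves N = 358, alpha and power unchanged. Passing the fixed 91% does not by itself show that the second test helped: a second test with no detection at all passes with probability from 0.05 to 0.99 as the PCR-positive share falls from 9% to 4%. Even where first-test NPV is exactly 91%, detecting about 47% of the remaining infections reaches the 95% target.

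The size depends on the PCR-positive share and on second-test specificity, both assumed and shown as ranges. The support from 21.1 depends on how that sentence is read and on 94% detection among first-test misses. The sensitivity analysis would reveal a useless test descriptively, but its formal version is unlikely to pass at the expected number of positives. This should be fixed before analysis; it does not threaten the design.

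**What to change.** In 20.1, replace *at least* with *at most* before 91% in the Aim 1 null.

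In 20.4, add for Aim 1:

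> First-test NPV (the PCR-negative share of all initial negatives in the Aim 1 set defined in 20.3) will be reported beside second-test NPV in the same participants, with the NPV gain and the missed infections per 100 initial negatives before and after the second test, each with a 95% CI from a participant-level bootstrap. Where a count is zero, the counts and an exact interval for the proportion will be given instead. NPV above 91% will be interpreted together with this gain. It will not be taken alone as evidence that the second test helps or that serial testing is non-inferior to PCR; that conclusion rests on the sensitivity and specificity tests.

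The exact interval is needed because the bootstrap collapses at zero: with 0 missed of 358 it gives 0 to 0, while the exact interval is 0 to 1.02 per 100.

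**Cost.** One phrase and a short descriptive addition using data already collected. N, alpha, power and procedures stay as they are, and no success criterion is added. A pass on 91% alone would support a narrower conclusion, and the gain will be imprecise with few positives: 3 of 7 detected with 4 false positives gives 347/351 − 351/358 = 0.8 points (95% CI 0.0 to 1.9). The change does not cure the shortage of PCR-positives for the sensitivity test; it only stops the NPV result from standing in for it.

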## PROTOCOL TITLE: SAFE AND HEALTHY SCHOOLS

subjects after a single test) versus the alternative hypothesis that the NPV is greater than 91%.

Aim 2: The lollipop swab test will be non-inferior to the gold-standard PCR testing of nasal swabs.

### 20.2 Sample Size Justification:

For Aim 1, it is anticipated that the majority of initial BinaxNOW tests will be negative. It is hypothesized that the proposed two-day serial testing procedure using BinaxNOW tests in participants with an initial negative test will identify true negatives in >95% of participants. The primary diagnostic outcome measure will be the negative predictive value (NPV). The NPV of BinaxNow is ~91% in symptomatic subjects. For the proposed study, the NPV after the second test (24 hours after the first negative results), is assumed to be substantially higher than 91% since the first test was already negative. In order to detect a true NPV after the second test of at least 95% with 90% power at the one-sided 0.05 significance level, a sample size of N=358 participants with an initial negative test is required. To reach a sample size of N=358 participants with an initial negative test, BinaxNOW kits will be administrated to 400 participants. We intend to continue enrolling until we reach the target sample size of N=358 completing the at-home BinaxNOW test.

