## 1.0 Study Summary

Study Title	Safe and Healthy Schools
Brief Summary	This study will target Madison Metropolitan School District school children ages 4-19 and staff who have not had a previous positive COVID-19 test within the past 3 months. It will enroll children and adults for 1-3 days to explore whether serial “at-home” BinaxNOW testing is feasible and non-inferior to “at school” single PCR testing for the evaluation of symptomatic individuals with a negative initial BinaxNOW. It will also explore whether lollipop swabs are more acceptable and perform as well as nasal swabs with PCR testing.
Number of study sites	1
Study Design	Community-based empirical research
Primary Objective	(1) Determine whether “at-home” BinaxNOW testing is feasible for families, (2) Evaluate whether serial “at-home” BinaxNOW testing is non-inferior to “at school” single PCR testing, (3) Compare the acceptability of lollipop swabs and nasal swabs, and (4) Compare the performance of lollipop swabs to nasal swabs with PCR-based testing.
Secondary Objective(s)	NA
Research Intervention(s)/ Investigational Agent(s)	NA
Drugs/devices used on study (including any IND/IDE #)	This study will evaluate the BinaxNOW COVID-19 Ag Card and the “lollipop” swab sample collection method
Study Population	Madison Metropolitan School District school children ages 4-19 and staff
Sample Size	400 with negative at-school BinaxNOW and 50 with positive at-school BinaxNOW. Total n=450.
Study Duration for individual participants	Up to 5 days
Study Specific Abbreviations/ Definitions	PCR: polymerase chain reaction EUA: emergency use authorization

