**Antigen testing:** Instead of detecting viral nucleic acids, the target for antigen tests is the nucleoprotein (N) protein of the SARS-CoV-2 virus. Antigen tests can be performed in a shorter time than PCR tests and are much less expensive. While antigen tests are less sensitive than PCR tests, they both detect individuals who are infectious. The Abbott company developed a very simple assay that has been commercialized for use both as point-of-care as well as an in-home test called the BinaxNOW-COVID-19 Antigen test (hereinafter call BinaxNOW). The test comes packaged within a card which is the size and shape of a credit card and which opens like a small book. In addition, there is a container of reagent. The reagent is delivered into a small hole in the card. A nasal swab is obtained from the patient by swirling the swab gently in the anterior nares several times. The swab is then inserted into the space where the reagent is located and turned several times. A positive test is indicated by the presence of 2 lines, very similar to home pregnancy tests. The testing time is 15 minutes. A positive swab can be detected within 5 to 8 minutes, but the test cannot be classified as negative until 15 minutes have elapsed. In addition, this test is CLIA-waived and can be performed by school health personnel in the school setting, eliminating the need for specimen transport and dramatically reducing turn-around-time and providing immediately actionable results for determining the need for exclusion from school.

The BinaxNOW test is reported to be approximately 94% sensitive in patients with symptomatic COVID-19 infections. Accordingly, it would be anticipated that if an individual who was truly infected with SARS-CoV-2 tested negative with the BinaxNOW test, then another test would almost certainly become positive if repeated within 24 hours, as the climb in viral load is particularly steep once

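### Rejecting the 91% null for Aim 1 would not show that the second BinaxNOW test adds anything, because on the plan's own expectations one test already exceeds 91%

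*Combined protocol and SAP*

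**What the plan says.** Section 20.1 sets the Aim 1 hypothesis around 91%: "The null hypothesis is that the negative predictive value of BinaxNOW is at least 91% (which is the reported rate in symptomatic" subjects, continuing that this is the rate after one test. The alternative is an NPV above 91%. (The null is worded as 'at least'; 91% is read here as its boundary.)

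Section 20.2 repeats the benchmark ("The NPV of BinaxNow is ~91% in symptomatic subjects") and reasons that NPV after a second test should be well above it. The size is set to "detect a true NPV after the second test of at least 95"%, "with 90% power at the one-sided 0.05 significance level", which gives N=358 participants with a negative first test. The same paragraph says that "it is anticipated that the majority of initial BinaxNOW tests will be negative".

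Other relevant statements:
- Section 2.3, antigen testing: "The BinaxNOW test is reported to be approximately 94% sensitive in patients with symptomatic COVID-19 infections". The figure is repeated under testing in schools as the reason a negative antigen test needs PCR follow-up.
- Section 2.3, opening: prevalence in school-aged children is described as unknown.
- Section 21.1: the chance of a positive home test is put below 5%.
- Section 20.4: sensitivity, specificity, PPV and NPV of the testing procedure are reported with 95% confidence intervals, and sensitivity and specificity are tested for non-inferiority. First-test NPV in the same participants is not listed.

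**The concern.** Because 91% is labelled the single-test value, a result above it will be read as evidence that the repeat home test improves on one test. That reading is sound only if single-test NPV among these participants really is near 91%.

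NPV depends on prevalence as well as on the test. If fewer attendees are infected than the 91% figure implies, a single negative test already has a higher NPV, and the hypothesis test can succeed with no contribution from the second test. The plan could then credit serial testing with a gain it did not produce, on the question that Aim 1.2 asks.

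**Working it through.** **1. Reproducing the plan's figure.** One-sample exact binomial test, null 0.91, alternative 0.95, one-sided 0.05, N=358:
- The critical count is 335 true negatives. P(X ≥ 335 | 0.91) = 0.0487.
- Power = P(X ≥ 335 | 0.95) = 0.909.
- The normal approximation gives N=352.

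So 358 and 90% power are correct for 91% against 95%.

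**2. Prevalence needed for a single-test NPV of 91%.** Let p be prevalence, Se = 0.94 (section 2.3) and Sp be specificity, which the plan does not give for BinaxNOW (assumed 95–100%).

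NPV = Sp(1−p) / [Sp(1−p) + (1−Se)p]. Setting this to 0.91:

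| Sp | p | first tests positive = Se·p + (1−Sp)(1−p) |
|---|---|---|
| 100% | 62.2% | 58.5% |
| 98% | 61.8% | 58.8% |
| 95% | 61.0% | 59.3% |

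Only about 41% of first tests would be negative. Section 20.2 expects a majority.

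**3. Single-test NPV if most first tests are negative.** The limiting case is 50% positive.
- Sp = 100%: p = 0.50/0.94 = 53.2%; NPV = (1 − 0.532)/0.50 = 93.6%.
- Sp = 95%: p = (0.50 − 0.05)/(0.94 − 0.05) = 50.6%; NPV = 0.95 × 0.494/0.50 = 93.9%.

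Single-test NPV is therefore at least 93.6% over the assumed specificity range.

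**4. The section 21.1 expectation.** Assume second-test sensitivity is also near 94%. Fewer than 5% positive home tests then means that fewer than 0.05/0.94 = 5.3% of first-test negatives are infected, so first-test NPV is above 94.7%. A true 91% would give 0.09 × 0.94 = 8.5% positive home tests.

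**5. What the 91% test would show if the second test detected nothing.** With Sp = 100%, all 358 stay negative and serial NPV equals first-test NPV. For first-test positive share s, the infected fraction among first-test negatives is q = (0.06/0.94) × s/(1−s).

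| s | first-test NPV = 1−q | missed infections = 358q | P(X ≥ 335) |
|---|---|---|---|
| 50% | 93.6% | 23 | 57% |
| 40% | 95.7% | 15 | 98% |
| 30% | 97.3% | 10 | >99.9% |
| 20% | 98.4% | 6 | ~100% |
| 11% | 99.2% | 3 | ~100% |

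At an NPV of 91% the number of missed infections would be 358 × 0.09 = 32. The 11% row mirrors the enrolment mix ("400 with negative at-school BinaxNOW and 50 with positive at-school BinaxNOW. Total n=450"; 50/450 = 11%). That mix is a quota, so the row is only an illustration.

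**The case against.** **The figures are external and approximate.** Both 94% and 91% are given as reported, rounded values, and may come from populations with different prevalence. The clash depends on the 94%: at an assumed 85% sensitivity, an NPV of 91% corresponds to 39–40% prevalence and 64–66% negative first tests, which agrees with a negative majority. This stands as a limit. But 94% is the only sensitivity the plan gives, and its rationale for repeat testing uses it. A benchmark from another population also cannot show what the second test adds in this one.

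**The section 21.1 figure can be reconciled with the design.** Moving from 91% to 95% needs the second test to find about 47% of missed infections: 0.91/(0.91 + 0.09 × 0.53) = 0.95. That gives 0.09 × 0.47 = 4.2% positive home tests, below 5%. This also stands, so step 4 holds only if second-test sensitivity is near 94%. Section 2.3 does expect a repeat test in an infected person to turn positive almost without fail. Step 3 does not use this assumption.

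**NPV is not the only Aim 1 analysis.** Section 20.4 also tests sensitivity and specificity. True, but section 20.2 names NPV as the primary diagnostic outcome and the size rests on it.

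**Stronger readings that the documents do not support:**
- A reader might infer that N=358 or the 90% power is wrong, or holds only if first-test NPV is 91%. The 94% is background and does not enter the calculation. Power is stated for any true NPV of at least 95% after the second test, and it rises with that value (99.0% at 96%, 99.97% at 97%).
- A reader might take 57% to more than 99.9% as an inflated type I error. If true NPV is 93.6%, concluding that it exceeds 91% is correct. The figures measure how little that conclusion says about the second test.

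**Conclusion.** The concern holds as a problem of interpretation, not of sample-size arithmetic. At 94% sensitivity, a 91% single-test NPV and a majority of negative first tests cannot both be true of this population. On the plan's own expectations one test already gives an NPV of at least 93.6%, and about 95% or more if the section 21.1 figure is combined with a second-test sensitivity near 94%. Success against 91% would then be more likely than not, and close to certain at 40% positivity or below, even with a home test that detects nothing.

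The conclusion rests on the 94% figure and on an assumed specificity of 95–100% (100% for the success probabilities and counts). It barely moves with specificity but is sensitive to sensitivity.

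**What to change.** 1. **Sections 20.1 and 20.2.** State that the 90% power is against an external benchmark of 91%, and that exceeding it does not by itself show a benefit of serial testing.
2. **Section 20.2.** State the expected number of infections missed by the first test among 358 over a range of first-test positivity: about 23 / 15 / 10 / 6 / 3 at 50 / 40 / 30 / 20 / 11% (94% sensitivity, 100% specificity), against 32 at an NPV of 91%.
3. **Section 20.4.** Add first-test NPV in the same Aim 1 participants, that is, the proportion nasal-PCR negative among at-school negatives, with its 95% confidence interval. Base any claim of improvement on the within-participant difference between serial and first-test NPV, with an interval that respects the pairing (for example a bootstrap over persons, since section 7.5 allows repeat enrolment). Report beside it the proportion of PCR-positive first-test negatives that the home test detects.

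The NPV estimated in this sample should not be inserted as a fixed null. It would be an estimate treated as known, and at 99.2% even 358 of 358 true negatives could not reject it (0.992^358 = 0.056).

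Cost: wording and one added analysis. Nasal PCR is already required for every Aim 1 participant, so no extra participants or data are needed. The downside is imprecision when few infections are missed: if the home test found all of 10, the exact 95% lower limit for detection would be 0.025^(1/10) = 69%; for all of 3 it would be 0.025^(1/3) = 29%.
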